6.1.5. Pooling of Sites

Not applicable.

6.1.6. Subgroup

The subgroup analyses of selected safety and efficacy endpoints will be based on the below subgroup variables at both primary baseline and OLE baseline:

- Age groups (9-11 years, 12-17 years, 18-64 years, and ≥ 65 years)
- Gender (Male vs. Female)
- Race (White, Black vs. Other)
- Ethnicity (Hispanic vs. Non-hispanic)
- Baseline IGA (3 vs. 4 for primary baseline, 0 or 1 vs. 2 vs. 3. vs. 4 for OLE baseline)
- Baseline BSA% ($<5\%$ vs. $\geq 5\%$)
- Baseline BSA% tertiles based on overall group

6.1.7. Derived Variables

- **IGA success** = IGA of “completely clear” or “almost clear” plus a 2-grade improvement from Baseline. For IGA success analysis, the subjects who achieved IGA of 0 or 1 at baseline will be excluded from the analysis.
- **Erythema success** = Erythema score of 0 or 1 plus a 2-grade improvement from Baseline as observed over time. For erythema success analysis, the subjects who achieved erythema score of 0 or 1 at baseline will be excluded from the analysis.
- **Scaling success** = Scaling score of 0 or 1 plus a 2-grade improvement from Baseline as observed over time. For scaling success analysis, the subjects who achieved scaling score of 0 or 1 at baseline will be excluded from the analysis.
- **Compliance** = number of applications divided by the expected number of investigational product (IP) applications for each subject. Compliance will be calculated using drug accountability data over the entire treatment period for each subject, up to treatment completion or discontinuation.
- **Number of expected IP applications** = calculated as last treatment date - first treatment date + 1. Excluding treatment-free interval time (defined in this section).
- **Number of IP applications** = number of expected IP applications – missed IP applications as collected in the CRF. Missed IP applications will not be taken into consideration in determining number of IP applications if the reason for missing dose is per investigator confirmation of clear.

- **Days on IP** = last date of IP application – first date of IP application +1. Subjects that stop taking IP per investigator confirmation of clear will be excluded from this calculation.
- **Treatment Gap** = This will be calculated for subjects belonging to Cohort 2 Group 3 that rolled into the extension study (ARQ-154-214) with a gap. This is derived start treatment start date in ARQ-154-214 – last treatment date in ARQ-154-203 + 1.
- **Treatment Duration (weeks)** = (last date of IP application – first date of IP application +1)/7.
- **Duration of IGA success** = The date of first observation where IGA does not meet success criteria - the date of first observation of IGA success + 1. The duration of IGA success for subjects who end treatment in IGA success will be censored at the last disease assessment date. Only the first duration of IGA success will be analyzed.
- **Duration of IGA of 0** = the date of first observation of IGA > 0 - the date of first observation of IGA of 0 and stop treatment. The duration of IGA of 0 for subjects who end treatment in IGA success will be censored at the last disease assessment date. This is for subjects who achieve IGA of 0 and stop the treatment. Subjects who achieve IGA of 0 but never stop treatment will be excluded from the analysis. For subjects who achieve IGA of 0 but stop the treatment later, the duration starts from the date of stop treatment. Only the first IGA of 0 duration will be analyzed.
- **Duration of IGA of 0 or 1** = the date of first observation of IGA > 1-the date of first observation of IGA of 0 or 1 + 1. The duration of IGA of 0 or 1 for subjects who end treatment in IGA of 0 or 1 will be censored at the last disease assessment date. Only the first IGA of 0 or 1 duration will be analyzed.
- **Disease recurrence** = the date of first observation of IGA of 2 or above after achieving IGA of 0 and stop treatment - the date of first observation of IGA of 0 + 1. Only the first disease recurrence will be analyzed.
- **Treatment-free interval** = the date of re-starting study drug due to IGA score above 0 - the date of stop treatment due to attainment of score of IGA of 0 +1, among subjects who achieve a “completely clear” IGA and stop treatment to all lesions. If subjects never re-start study drug after stopping treatment, the treatment-free interval is censored at the end of study date. Only the first treatment-free interval will be analyzed.
- **Weight of IP (g)** = dispensed can weight – returned can weight.
- **BMI (kg/m²)** = (weight in kg)/[(height in cm/100)²]. Day 1 height will be used for BMI derivation upto Week 24. For visits including week 24 through week 36, week 24 height

will be used to derive BMI. Week 52 BMI is derived using the height and weight collected at the same visit. This derivation is applied since height is not collected at all visits.

- **BMI Categories:**

- Underweight: $BMI < 18.5$
- Normal: $18.5 \leq BMI \leq 24.9$
- Overweight: $25.0 \leq BMI \leq 29.9$
- Obese: $BMI \geq 30.0$

- **WI-NRS 4-point reduction** = achievement of a 4-point reduction in WI-NRS pruritus score post-baseline compared to baseline, calculated only for subjects with a pruritus score of ≥ 4 at baseline.
- **Itch-free state** = achievement of in WI-NRS of 0 or 1.
- **PHQ-8** = sum of the 8 questions (individual questions scored as Not at all=0, Several days=1, More than half the days=2, and Nearly every day=3; range for score 0 to 24). If more than 1 item is missing the score should not be calculated. If 1 item is missing the score is calculated as (sum of answered items*8)/number of answered items.
- **PHQ-A** = sum of the 8 questions (individual questions scored as Not at all=0, Several days=1, More than half the days=2, and Nearly every day=3, (range for score 0 to 24). If more than 1 item is missing, the score should not be calculated. If 1 item is missing, the score is calculated as (sum of answered items*8)/number of answered items.
- **CDI-2** = total score is calculated as a sum of the 17 questions (individual questions scored as much or most of the time=3, often=2, some of the time=1, Not at all=0; range for score 0 to 51).
 - CDI-2 emotional problem scale is a sum of 9 questions (Q1, Q3-6, Q8, Q10 -12)
 - CDI-2 function problem scale is a sum of 8 questions (Q2, Q7, Q9, Q13-17)
- **Scalpdex score transformation** = Scalpdex is rated on a 1 to 5 scale which will be transformed to 0 to 100 Scale where 1=0; 2=25; 3=50; 4=75; 5=100. This transformed score is used to calculate scale scores.
- **Scalpdex Emotions Scale** = average of (Q2, Q4, Q5, Q6, Q7, Q9, Q10, Q11, Q12, Q14, Q16, Q17, Q19, Q20, Q22) after transforming to 0 to 100 scale as mentioned above.

Q refers to question number. Q19 will be reverse scored i.e., 1=100; 2=75; 3=50; 4=25; 5=0.

- **Scalpdex Symptoms Scale** = average of (Q1, Q3, Q8) after transforming to 0 to 100 scale as mentioned above. Q refers to question number.
- **Scalpdex Functioning Scale** = average of (Q13, Q15, Q18, Q21, Q23) after transforming to 0 to 100 scale as mentioned above. Q refers to question number.
- **Scalpdex Total Score** = calculated as mean of all the 23 scalpdex questions using the transformed scale of 0 to 100. Q19 will be reverse scored i.e., 1=100; 2=75; 3=50; 4=25; 5=0 while calculating the mean. Q refers to question number.
- **Total % BSA (body surface area)** = sum of coverage areas of head, limbs, upper limbs, and lower limbs.
- **Change from baseline** = value at current time point – value at baseline. This is derived separately for primary baseline and OLE baseline.
- **Percent change from baseline** = (value at current time point – value at baseline)/value at baseline. This is derived separately for primary baseline and OLE baseline.
- **TEAE** = any AE that started after application of IP at the Baseline Visit in this extension study, or in parent study through completion.
- **C-SSRS Suicidal Ideation** = A “yes” answer at any time during treatment to any one of the five suicidal ideation questions (Categories 1-5: Wish to be Dead, Non-specific Active Suicidal Thoughts, Active Suicidal Ideation with Any Methods (Not Plan) without Intent to Act, Active Suicidal Ideation with Some Intent to Act, without Specific Plan Active Suicidal Ideation with Specific Plan and Intent).
- **C-SSRS Suicidal Behavior** = A “yes” answer at any time during treatment to any one of the five suicidal behavior questions (Categories 6-10: Preparatory Acts or Behavior, Aborted Attempt, Interrupted Attempt, Actual Attempt (non-fatal), Completed Suicide).

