7.6. Exposure and Compliance

The number of IP applications by each subject based on diary data will be summarized using descriptive statistics appropriate for continuous variables.

The amount of IP used by each subject based on can weight will be summarized descriptively using continuous methods.

The number of days on IP will be derived as indicated in Section [6.1.7](#) and summarized descriptively.

The gap between completing study ARQ-151-203 and enrolling into this study will not be included in the above definition and will be summarized separately for subjects in Cohort 2 Group 3.

A subject will be considered compliant with the dosing regimen if the subject applies at least 80% of the expected applications during the IP application period and does not miss more than 3 consecutive doses. Doses missed due to IGA clearance were not considered as noncompliance.

AD-ST-33.06 Effective date: 12-Nov-2020

The number and percent of subjects that missed more than 3 consecutive doses will be tabulated except for subjects who withheld IP application due to IGA clear per investigator.

Investigational product application compliance will be calculated based on number of applications divided by the expected number of IP applications. Compliance will be summarized descriptively using the following categories:

- > 100%
- $\geq 80\% - \leq 100\%$
- < 80%

Drug exposure and compliance will be presented using primary and OLE baselines. The number of subjects with treatment duration (≥ 1 day, ≥ 8 weeks, ≥ 12 weeks, ≥ 24 weeks, ≥ 32 weeks, ≥ 54 weeks, and ≥ 62 weeks) will also be summarized similarly. Study duration will be summarized from primary and OLE baseline.

Similar exposure and compliance information will be summarized for subjects who completed or discontinued study before protocol amendment 1.

8. Efficacy Analysis

This study is open label without a comparator group; therefore, there will be no formal hypothesis testing performed in the study.

For the continuous variables, the number of nonmissing values and the mean, SD, minimum, Q1, Q3, median, and maximum will be tabulated by study visit; similarly, categorical variables will have the counts and proportions of each value will be tabulated by study visit.

For efficacy summaries 2 baselines will be used (primary and OLE) using Safety population as defined in Section [6.1.1](#).

All efficacy summaries for primary and OLE baselines will be presented as indicated below:

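### The SAP 7.6 exclusion of the between-study gap is not carried into the SAP 6.1.7 formulas, so primary-baseline treatment duration and compliance count off-drug days for Group 3 subjects previously on roflumilast

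*SAP*

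**What the plan says.** SAP 7.6 states: "Drug exposure and compliance will be presented using primary and OLE baselines". Under SAP 6.1.1, primary baseline precedes the first roflumilast dose in either the parent study or this one. For Group 3 subjects from the roflumilast arm of ARQ-154-203, that dose was given in the parent study.

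The relevant definitions in SAP 6.1.7 are:

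- Expected IP applications: "calculated as last treatment date - first treatment date + 1. Excluding treatment-free interval time". The treatment-free interval starts from "the date of stop treatment due to attainment of score of IGA of 0 +1", so it is a pause for clearance within treatment.
- Number of IP applications: "number of expected IP applications – missed IP applications as collected in the CRF".
- Treatment Duration (weeks): "last date of IP application – first date of IP application +1)/7" (opening bracket omitted), with nothing subtracted.
- Treatment Gap, for Group 3: the ARQ-154-214 start date minus "last treatment date in ARQ-154-203 + 1". No other formula in 6.1.7 uses it.

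SAP 7.6 deals with the gap once, directly after pointing to 6.1.7 for days on IP: "The gap between completing study ARQ-151-203 and enrolling into this study will not be included in the above definition". It then says the gap is summarized separately for Group 3. Compliance and the treatment-duration rows (up to ≥54 and ≥62 weeks) come later in the section with no such statement. SAP 7.6 also describes the application count differently: "The number of IP applications by each subject based on diary data".

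**The concern.** Days on IP and Treatment Duration are the same span in different units, yet only the first is expressly made gap-free. A programmer who follows the text could report one subject with 421 days on IP and a Treatment Duration that also contains the whole interval between studies. The treatment-free interval cannot repair this, because it begins with a stop for IGA 0.

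The long-duration rows matter here. SAP 3.2 says the sample size does not rest on power or precision, and both SAP 3.2 and Protocol 7.1.2 justify it partly by its contribution to ICH exposure goals. Off-drug time in the top rows would overstate how many subjects have long exposure. The same days also enter the denominator of the compliance ratio.

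**Working it through.** **Inputs.** The ARQ-154-203 Week 8 target is day 56, and the OLE targets are study days 29, 85, 169, 253 and 365 (SAP Tables 2 and 3). The duration rows and the 80% compliance boundary are in SAP 7.6. The number of off-drug days, G, is not given, so the values of G below are assumptions or break-even points. For simplicity, no stop for IGA 0 is assumed.

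**1. The plan's own time scale.** Table 2 targets should equal 56 plus the OLE day: 56+29 = 85, 56+85 = 141, 56+169 = 225, 56+253 = 309, 56+365 = 421. All five match, so Table 2 leaves the gap out. A gap-free completer has 421/7 = 60.1 weeks, or 428/7 = 61.1 weeks with the +7-day visit window. The ≥62-week row needs 62×7 = 434 days. Even if the parent period ran to day 61, the end of Table 2's Week 8 window, the total would be 61+372 = 433 days.

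**2. Treatment Duration as written, from primary baseline.** The span is 56 + G + OLE days.

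| OLE days | G (days) | Treated | Span by formula | Top row reached |
|---|---|---|---|---|
| 365 | 0 | 421 d (60.1 wk) | 421 d (60.1 wk) | ≥54 |
| 365 | 13 | 421 d (60.1 wk) | 434 d (62.0 wk) | ≥62 |
| 365 | 84 | 421 d (60.1 wk) | 505 d (72.1 wk) | ≥62 |
| 365 | 182 | 421 d (60.1 wk) | 603 d (86.1 wk) | ≥62 |
| 169 | 0 | 225 d (32.1 wk) | 225 d (32.1 wk) | ≥32 |
| 169 | 153 | 225 d (32.1 wk) | 378 d (54.0 wk) | ≥54 |

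The break-even gaps are 434 − 421 = 13 days and 378 − 225 = 153 days.

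**3. Compliance, for a completer with 100 missed doses (illustrative).** The gap-free value is (421−100)/421 = 321/421 = 76.2%. With the gap in the denominator:

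| G (days) | 6.1.7 numerator: expected minus CRF-missed | Diary numerator: doses actually applied |
|---|---|---|
| 84 | 405/505 = 80.2% | 321/505 = 63.6% |
| 182 | 503/603 = 83.4% | 321/603 = 53.2% |

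The first column assumes that no gap day is recorded as missed in the CRF. On the diary basis, a subject who missed nothing would score 421/505 = 83.4% or 421/603 = 69.8%.

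**4. Treatment Gap.** Off-drug days are start − last − 1. The SAP's start − last + 1 is therefore G + 2. Dosing on consecutive days (start − last = 1) gives 2 where the answer is 0. If this variable were subtracted from the span, a completer would be left with 421 + G − (G + 2) = 419 days instead of 421.

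**The case against.** The strongest reply is that the SAP plainly intends gap-free counting. SAP 7.6 excludes the gap and reports it separately. SAP 6.1.4 says the gap is not counted in the Group 3 visit windows, and Table 2 adds parent and extension days without it. The 24/32 and 54/62 week rows each differ by 8 weeks, which fits adding the parent period to time in this study. The 7.6 sentence also follows three measures (applications, amount used, days on IP), so a sympathetic reader could extend it to all of them. All of this stands as evidence of intent. It does not change the formulas. The exclusion refers to a single definition and directly follows days on IP, while the duration rows and compliance ratio rest on 6.1.7 formulas without it.

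A reader might infer more: that the SAP sets out to count the gap as treated time and applied doses throughout Group 3, inflating exposure and compliance. The documents do not support that.

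- **Scope.** For Group 3 subjects from the vehicle arm, primary baseline equals OLE baseline (SAP 8), so no gap falls inside the span. OLE-baseline tables are unaffected for everyone.
- **Doses and compliance.** Gap days become applied doses only under the 6.1.7 derivation. Section 7.6 says the count comes from diary data, which would not show doses in the gap, and compliance would then be understated.
- **The 80% boundary.** Crossing it changes the compliance category. Being classed as compliant also requires no more than 3 consecutive missed doses, so a ratio above 80% is not enough.
- **Treatment Gap.** No stated formula subtracts it, so its 2-day error affects only the gap summary unless someone uses it as a correction.

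**Conclusion.** The definitions are wrong as written, for a limited set of subjects and tables: Cohort 2 Group 3 subjects previously on roflumilast, in primary-baseline summaries. Section 6.1.7 does not say which study supplies the first date. The conclusion takes it from ARQ-154-203, which is what presenting from primary baseline implies for these subjects.

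On that basis, Treatment Duration is overstated by exactly the off-drug days. Thirteen such days put a completer in a row that an in-window gap-free completer cannot reach. Expected applications carry the same excess. The error in compliance has no fixed direction until the source of the application count is settled. How many subjects would change rows cannot be stated. This is a failure to carry an intended exclusion into the formulas, and it should be corrected because long-duration exposure is a main output of the study.

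**What to change.** In SAP 6.1.7, for Group 3 subjects previously on roflumilast and under primary baseline, compute Treatment Duration, expected applications and applications as the sum of the ARQ-154-203 and ARQ-154-214 on-drug periods, with first and last dates defined per study. Redefine Treatment Gap as the ARQ-154-214 first treatment date minus the ARQ-154-203 last treatment date minus 1.

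In SAP 7.6, state that the gap exclusion covers treatment duration, applications and compliance as well as days on IP. Correct the parent study number there from ARQ-151-203 to ARQ-154-203. Name one source for the application count, and align 6.1.7 with it, including its statement that compliance uses drug accountability data.

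The cost is a few lines of SAP text and minor programming with dates already held. The ≥54 and ≥62 week counts may come out lower.

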5.6.4. Treatment Compliance

Weight of the IP applied will be measured for reporting purposes. Each IP Can will be weighed individually at each follow-up clinic visit and recorded in the source notes and in the eCRF.

Subjects will complete a daily diary recording the date and time of each dose applied, any missed doses, and a comment section should the subjects have a comment, e.g., record potential Adverse Events (AEs). Site personnel will review the diaries at each clinic visit and use the information to question the subject regarding compliance and AEs and then record appropriate information in source documents and complete Case Report Forms (CRFs). If a subject misses a scheduled dose, they should be instructed to return to the protocol IP administration schedule (i.e. if subject forgets a dose they should wait until that evening and apply as usual).

A subject will be considered compliant with the dosing regimen if the subject applies at least 80% of the expected applications during the IP application period and does not miss more than 3 consecutive doses.

Compliance will be assessed by review of the dosing diary. If the diary shows less than 80% of expected use, the subject is using too little IP and retraining must be conducted and documented.

Compliance will be documented in source and in eCRF.

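### Compliance runs to an undefined last treatment date and subtracts missed doses with no matching window, so the percentage can be wrong for subjects who stop applying the foam

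*SAP*

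**What the plan says.** SAP 6.1.7 builds compliance from three definitions.

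- Expected applications are "calculated as last treatment date - first treatment date + 1", excluding treatment-free interval time.
- Applications are the "number of expected IP applications – missed IP applications as collected in the CRF". Missed doses are disregarded only "if the reason for missing dose is per investigator confirmation of clear".
- Compliance is applications divided by expected applications, calculated "over the entire treatment period for each subject, up to treatment completion or discontinuation".

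The same list uses other end dates. Days on IP is "last date of IP application – first date of IP application +1", a different term from the one used for expected applications. Treatment Gap, however, uses the expected-applications term for the end of dosing in ARQ-154-203. For a subject who never restarts after clearing, the treatment-free interval is censored at the end-of-study date.

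The missed-dose data start in the diary. Protocol 5.6.4 states: "Subjects will complete a daily diary recording the date and time of each dose applied, any missed doses".

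SAP 7.6 reports compliance descriptively and in categories cut at 80% and 100%. A subject counts as compliant who "applies at least 80% of the expected applications during the IP application period and does not miss more than 3 consecutive doses". It adds: "The number and percent of subjects that missed more than 3 consecutive doses will be tabulated", with an exception for doses withheld because the investigator confirmed clear.

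**The concern.** A ratio of applied to expected doses needs one period for both counts. Here the end of the expected count is undefined, and the missed-dose count has no stated window. If the expected count ends on the last dose, the days of a terminal lapse are not in it. The CRF may still hold those days as missed doses. They are then subtracted from a base that never contained them; if they are not recorded, the lapse disappears. Neither result describes compliance up to completion or discontinuation.

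The same mismatch reaches subjects who follow the protocol. Protocol 5.6.3 has cleared subjects stop applying the product. If they never restart, a treatment-free interval running to the end of the study is removed from a span that closed at the last dose.

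At stake are the compliance percentages, the 80% categories and, in some cases, the reported number of applications.

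**Working it through.** The plan states no compliance figure to reproduce, so the check applies the SAP 6.1.7 formulas directly.

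**Inputs.** Dosing is once daily for up to 52 weeks (SAP 3.1), and Week 52 is Day 365 (SAP Table 1). Illustrative assumptions: daily use from Day 1 to Day L, none afterwards, not confirmed clear, no earlier misses, and a treatment period ending on Day E.

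**Formulas.**

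- A. Expected count ends at the last dose and the lapse is not recorded: L / L.
- B. Expected count ends at the last dose and the lapse is recorded as missed: [L - (E - L)] / L.
- C. Both counts end at Day E and the lapse is recorded: [E - (E - L)] / E = L / E.

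**Short example, L = 40, E = 100.** Expected under A and B is 40 - 1 + 1 = 40.

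- A: 40/40 = 100%.
- B: applications = 40 - 60 = -20; compliance = -20/40 = -50%.
- C: (100 - 60)/100 = 40%.

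**Full-length follow-up, E = 365.**

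| Last dose (L) | A | B | C |
|---|---|---|---|
| Day 100 | 100% | -165.0% | 27.4% |
| Day 200 | 100% | 17.5% | 54.8% |
| Day 300 | 100% | 78.3% | 82.2% |
| Day 351 | 100% | 96.0% | 96.2% |

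B is negative only when L < E/2, here L up to 182. It reaches 80% when L is at least 365/1.2, so from Day 305. C reaches 80% at 0.8 × 365 = Day 292. A last dose on Days 292 to 304 is therefore classed differently by B and C. A puts every such subject at 100%.

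**Earlier misses.** With 10 misses before a last dose on Day 100 and E = 365, A is 90/100 = 90.0%, B is (100 - 10 - 265)/100 = -175.0%, and C is (365 - 10 - 265)/365 = 24.7%.

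**Cleared subject who never restarts.** Assume the last dose and stop date are both Day 100 and the study ends on Day 365. The treatment-free interval is 365 - 100 + 1 = 266. With the span closed at the last dose, expected applications = 100 - 266 = -166. Doses missed because of clearance are disregarded, so applications are also -166 and the ratio is 100% only because the signs cancel. With 10 earlier misses the ratio is (-166 - 10)/(-166) = 106.0%, whereas 90 of 100 due doses is 90%.

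**The case against.** The strongest reply is that the SAP never says expected applications stop at the last dose. It uses a different term for Days on IP, and the compliance definition itself names completion or discontinuation as the end of the period. Read together, these allow the last treatment date to be that end date, and the example then gives the correct 40%. This stands as a possible reading. The Treatment Gap usage points the other way, and nothing in the SAP settles it. The reading also works only if the lapse days are recorded as missed.

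Further points stand:

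- No text says the CRF logs missed doses after dosing has ceased. The negative lapse result needs both the last-dose reading and that recording practice.
- A reader might infer that every such subject scores either 100% or below zero. That does not follow: 100% requires no earlier misses, and later recorded lapses give positive values that are biased low, sometimes only slightly.
- A reader might infer that the application count is always wrong for subjects who lapse. If the lapse is unrecorded and the span ends at the last dose, the count is right (40 in the example).
- The 40% assumes that dosing was still due to Day 100. Protocol 5.4.3 and 5.4.4 separate stopping the product from leaving the study. For a subject who discontinued the product on Day 40, 40/40 is correct.
- If the lapse is recorded, the rule on more than 3 consecutive missed doses still flags the subject. It does not repair the percentage or its category.

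**Conclusion.** The point holds as a minor definitional gap. On the most natural reading of the last treatment date, compliance is inflated when a terminal lapse is unrecorded. It is biased low when the lapse is recorded, and negative when recorded misses exceed expected doses. On the same reading, expected applications can be negative for a subject who clears and never restarts. The size depends on when the subject stops: 100% or -165.0% against 27.4% for a last dose on Day 100 of 365, but 96.0% against 96.2% for Day 351 when the lapse is recorded.

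These figures rest on illustrative stopping days, and the documents do not show how many subjects would be affected. A reader might infer that the exposure evidence, or the safety conclusion, is undermined. The documents do not support that. SAP 7.6 separately summarises days on IP, can weight and treatment duration. No endpoint or analysis population uses compliance, and the study plans no inference. The effect is confined to the compliance summary and its 80% categories, together with the application count where post-lapse misses are recorded or where a clear interval is subtracted beyond the span.

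**What to change.** In SAP 6.1.7, define one closing date for each subject: treatment completion, or the documented discontinuation of IP. State how that date is set for a subject who lapses and does not resume. Count both expected and missed applications from the first treatment date to that closing date.

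Exclude every investigator-confirmed clear interval, but only for days inside the window. *Every* matters because the SAP analyses only the first treatment-free interval. If the exclusion follows that rule, later clear days stay in the expected count while their missed doses are disregarded, so they are counted as applied.

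Counting applied doses directly from the diary is optional once the windows match. Its advantage is that the result no longer depends on every missed day having been entered.

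The cost is SAP wording and programming, with no new data collection. Reported compliance may be somewhat lower.

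### Expected IP applications exclude a treatment-free interval that is defined for Kaplan-Meier use; used as cross-referenced, it miscounts applications and compliance for subjects with repeated or unended clear periods

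*SAP*

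**What the plan says.** All the definitions are in SAP 6.1.7.

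- Expected applications: "calculated as last treatment date - first treatment date + 1. Excluding treatment-free interval time (defined in this section".
- Treatment-free interval: the restart date minus "the date of stop treatment due to attainment of score of IGA of 0 +1". If the subject never restarts, it is censored at the end-of-study date. The entry closes with "Only the first treatment-free interval will be analyzed".
- Number of applications: "number of expected IP applications – missed IP applications as collected in the CRF", with the rider that missed doses "will not be taken into consideration in determining number of IP applications if the reason for missing dose is per investigator confirmation of clear".
- Compliance: "number of applications divided by the expected number of investigational product (IP) applications for each subject".

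SAP 7.6 calls a subject compliant who "applies at least 80% of the expected applications during the IP application period and does not miss more than 3 consecutive doses", and adds that doses missed because of clearance are not noncompliance.

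Protocol 5.6.3 has clearance judged at every clinic visit. IP stops when the subject is clear and restarts when disease returns, and protocol 6.5 adds unscheduled visits to confirm clearance. A subject can therefore go through more than one clear period in 52 weeks. Nothing in the SAP says that the intervals are summed when expected applications are derived.

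**The concern.** The expected count borrows a variable built for a time-to-event analysis. A time-to-event variable can reasonably take one episode per subject and censor at study end. A deduction from an application count needs every off-treatment day inside the dosing span and no day outside it.

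The missed-dose rider makes the gap matter. A day on which IP was withheld for clearance has to leave the calculation somewhere. If it is not removed from the expected count, and the rider stops it being deducted as missed, it ends up as an applied dose.

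At stake are two planned summaries in a study whose objective is long-term safety: the number of applications and application-based compliance. For subjects who cleared, the application count is the main day-based measure that tries to net out time off drug. Treatment duration removes no clear time, and days on IP leaves these subjects out.

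**Working it through.** The documents give no figure on this point, so there is nothing to reproduce. The check applies the SAP 6.1.7 formulas to assumed inputs.

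**Notation.** S = days from first to last treatment, inclusive. T1 = first clear interval. T2 = later clear intervals in total. M = genuine misses (not due to clearance). E = expected applications, N = number of applications, C = N/E.

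**Part 1: subject with more than one clear interval, all ended by a restart**

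- Only the first interval removed: E = S − T1; N = S − T1 − M; C = 1 − M/(S − T1).
- All intervals removed: E = S − T1 − T2; N = S − T1 − T2 − M; C = 1 − M/(S − T1 − T2).

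The two values of N differ by exactly T2, whatever M is. The two values of C are both 100% when M = 0 and differ only when M > 0.

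Assumptions: S = 365, T1 = 56, T2 = 28, 56 or 84. With only the first interval removed, E = 365 − 56 = 309. At M = 60, N = 249 and C = 249/309 = 80.6%.

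| T2 | E, all removed | Excess in N | Excess as % of N, M = 0 | Excess as % of N, M = 60 | C, all removed, M = 60 | Excess in C, M = 60 | M at which the 80% limit flips to pass |
|---|---|---|---|---|---|---|---|
| 28 | 281 | 28 | 28/281 = 10% | 28/221 = 13% | 221/281 = 78.6% | 1.9 points | 57 to 61 |
| 56 | 253 | 56 | 56/253 = 22% | 56/193 = 29% | 193/253 = 76.3% | 4.3 points | 51 to 61 |
| 84 | 225 | 84 | 84/225 = 37% | 84/165 = 51% | 165/225 = 73.3% | 7.2 points | 46 to 61 |

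With fewer misses the effect on compliance is smaller: 0.3 to 1.2 points at M = 10 and 1.0 to 3.6 points at M = 30, over the same range of T2. The flips concern the 80% limit alone. The rule on consecutive missed doses is a separate condition and is not modelled here.

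**Part 2: subject who stops for clearance and never restarts**

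The span ends at the last dose, while the censored interval runs from then to study end. Assume first dose on day 1, stop date equal to last dose date, and study end on day 365.

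- Last dose day 169: interval = 365 − 169 + 1 = 197; E = 169 − 197 = −28.
- Last dose day 253: interval = 365 − 253 + 1 = 113; E = 253 − 113 = 140, against 253 days in the span.

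The error here is downward, and one interval is enough to produce it. Compliance also falls when there are misses. In the second case with M = 10, it is 130/140 = 92.9% against 243/253 = 96.0%.

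**Part 3: the end days**

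Restart minus stop plus 1 counts both end dates as treatment-free. If the stop date is the first day without IP, the days withheld are restart − stop, and the formula removes one treated day too many. If the stop date is the last day of application, the days withheld are restart − stop − 1, and the formula removes two too many. This is small, but it recurs for each interval.

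**The case against.** The strongest reply is that the SAP does not define the interval as the first one. The closing sentence selects an episode for analysis, and the same sentence form ends the neighbouring duration variables. The missed-dose rider makes sense only if every clear day has already left the expected count, and SAP 7.6 forgives doses missed for clearance with no first-episode limit. On that reading there is no overstatement. Likewise, time after the last dose cannot be excluded from a span that ends at the last dose, and a negative expected count shows that literal subtraction was not intended.

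Much of this stands. The intent is probably to exclude all clear days within the span. A reader might infer that the SAP prescribes first-interval-only exclusion and so overstates exposure and compliance generally. The documents do not support that: the restriction is worded as an analysis rule, compliance moves only when there are genuine misses, and the never-restart case errs the other way.

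The reply does not remove the problem. The cross-reference leads to one variable, which is a single interval with a censoring rule, and no instruction to sum or truncate is given. A programmer who reuses it gets wrong counts.

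The objection is also right on reach. Can weight is measured, treatment duration removes no clear time, and days on IP excludes subjects who stopped for clearance, so none of these depends on the rule. The TEAE and SAE endpoints are subject counts, and no analysis population is defined by compliance.

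**Conclusion.** The point holds as a defect in the derivation as cross-referenced, confined to number of applications and application-based compliance.

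- Later clear intervals: the application count is too high by exactly the number of later clear days. Under the assumed 365-day span and 56-day first interval, that is 28 to 84 applications for later intervals of 28 to 84 days. Compliance is too high by 0 points with no misses and by 1.9 to 7.2 points with 60. The 80% limit changes only in a narrow band of misses.
- No restart: expected applications are too low, possibly below zero.

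The interval lengths and miss counts are assumptions. The documents do not say how many subjects will clear, stop and restart more than once, so the effect on group summaries cannot be sized. It would be wrong to conclude that exposure in general is overstated, or that the safety endpoints are affected. The correction is still worth making before programming: the derivation can give impossible values, and the remedy is almost free.

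**What to change.** Replace the expected-applications entry in SAP 6.1.7 with a self-contained rule:

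*Expected applications = (last treatment date − first treatment date + 1) minus all days between first and last application on which IP was withheld for investigator-confirmed clearance, summed over all such intervals. Stop or restart days on which IP was applied are not subtracted.*

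In the treatment-free interval entry, state that the restriction to the first interval and the censoring at end of study apply to the Kaplan-Meier analysis only. The missed-dose rider can then stay, because every clear day within the span has already been removed once.

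Add a programming check that expected applications are at least 1 and that the number of applications lies between 0 and the expected number.

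The cost is a few lines of SAP text and the matching derivation specification. Protocol 5.6.4 has a daily diary of doses and missed doses, and SAP 6.1.7 relies on missed doses in the CRF with a reason, so no new collection should be needed. The sponsor should confirm that the CRF holds stop and restart dates for every clear interval, not only the first. Study conduct does not change.
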